## Uploads

Upload the entire grant application(s)

[name] r61 r33.pdf

Upload copy(ies) of unbolded Consent Form(s)

CF 11 23 18 Clean.pdf

Upload copy(ies) of bolded Consent Form(s)

CF 11 23 18 Bold.pdf

Upload copy(ies) of recruitment materials/ads to be reviewed

flyer 1.pdf

flyer 2.pdf

Flyer 3.pdf

Upload evidence of FDA Radiolabeled Drug approval(s)

Upload copy(ies) of JRSC approval(s)

Upload copy(ies) of the HIPAA form

HIPAA.pdf

Upload any additional documents that may be related to this study

MRI\_result\_letter\_1\_no\_findings.pdf

MRI\_result\_letter\_2\_followup.pdf

MRI\_result\_letter\_3\_irregular.pdf

IRB Subaward Contracts.pdf

Dosimetry table.pdf

RecruitMe text.pdf

Consent Procedure Note 7733.pdf

Study May Proceed (141742).pdf

form of notice.pdf

Statistical Analysis Plan

Targeting Dopaminergic Mechanisms of Slowing to Improve Late-Life Depression

IRB #7733

NCT #03761030

Date: 07/24/15

Overview: All variables at all time points will be examined for illegitimate values, outliers, and inconsistencies. The distribution of demographic variables and baseline clinical characteristics will be examined and described across the two randomized patient groups (N=45 each) in terms of means, standard deviations, proportions, and 95% confidence intervals. Indications of inequality between groups in specific features (despite randomization) will trigger examination of whether differences in primary outcome measures can be attributed to an imbalance in group assignment. Intent-to-treat will be used for analyses including all participants who are randomized and have at least one post-baseline HRSD score. Tests will be two-sided and statistical significance determined at p-value < 0.05.

Missing data: We will make every effort to obtain all data. The longitudinal mixed modeling described below is valid if missing data are missing at random (MAR). MAR assumptions cannot be verified. A 2010 national expert panel (166) recommended sensitivity analyses for the impact of missing data via pattern mixture models (167), which we will conduct (e.g., by investigating robustness of results to perturbations of assumed values for missing data within clinically plausible ranges).

Analyses for Aim 3: Aim 3.1: To determine whether L-DOPA administration results in greater improvements in depressive symptoms on the HRSD, a longitudinal mixed effects model will be used to analyze group differences using SAS Proc Mixed Version 9.3. The change in 24-item HRSD from baseline will be analyzed as a function of time, treatment group, the interaction between time and treatment, and baseline HRSD. Contrasts of mean difference in HRSD at each week will be formed and tested. Aim 3.2: To determine whether greater increases in processing and gait speed are associated with greater HRSD improvement, change scores from baseline to 8 weeks will be calculated for both processing and gait speed. Pearson correlation among all change scores, including change in HRSD will be examined, and two-sample t-tests will be used to assess treatment group differences. Multivariate linear regression models will be fit with change in HRSD as the outcome predicted by treatment, processing and gait speed change scores, and baseline values of processing and gait speed.

Exploratory aims: Inflammatory markers and COMT genotype will be tested as moderators of the L-DOPA effect on HRSD change by including their interactions with treatment in the Aim 3 analyses.

Power analysis: Aim 3.1: With N=45 per treatment group, and assuming a drop out of 15%, using two-sided test with $\alpha=0.05$, we have >80% power to detect treatment group differences with ES = 0.60 or greater. Given expected SD=5 points based on similar previously conducted studies in the LLDRRC, this ES would correspond to a change in HRSD of 3 points, which is smaller than the 4 point change considered meaningful. Aim 3.2: With N=90, assuming a drop out of 15%, we would be able to detect correlations >0.31. Thus, we have adequate power to detect a moderate to large correlations between change in HRSD and change in processing and gait speed.

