## Specific Aims and Hypotheses

### Specific Aims and Hypotheses

We hypothesize that treatment with levodopa (L-DOPA) will improve depressive symptoms in LLD by enhancing striatal dopamine release and improving cognitive/motor slowing. In the R33 Phase, 90 adults aged > 60 years with (1) a DSM 5 depressive disorder, (2) significant depressive symptoms (CES-D > 10), and (3) decreased processing speed (0.5 SD below age-adjusted norms on the Digit Symbol Test or Trails A) or decreased gait speed (average walking speed over 15' course < 1m/s) will be receive 8 weeks of treatment with LDOPA 450mg. Subjects will be tested for engagement of molecular target by determining whether subacute (8 week) treatment with L-DOPA displaces [C]-raclopride on positron emission tomography (PET).

R33 Phase.

Aim 1: To determine whether L-DOPA improves depressive symptoms in older adults.

Hypothesis 1: Compared to placebo, L-DOPA administration will result in greater improvements in depressive symptoms (as measured by HRSD scores).

Hypothesis 2: Greater post-L-DOPA decreases in [C]-raclopride BP and increases in processing/gait speed will be associated with greater depressive symptom improvement.

Exploratory aims: To explore the role of inflammatory markers and Catechol-O-methyl-transferase (COMT) genotype in moderating L-DOPA induced changes in slowing and depressive symptoms.

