### Assessments

21. Subjects are expected to have a screening/evaluation visit, pre-treatment PET/MRI scanning day(s) (for those receiving imaging), and weekly visits from Week 0-8.

22. The following measures will be collected weekly throughout the study: 24-item HRSD, CGI Severity and Improvement, Structured Pill Count Interview, Unified Parkinson's Disease Rating Scale (UPDRS) (questions 32 and 33 will be used in this study to assess the duration and disability of dyskinesias caused by L-DOPA), Treatment Emergent Side Effect Scale, and Inventory of Depressive Symptoms—Self Report (IDS-SR).

23. In addition, baseline processing and gait speed assessments will be repeated after **Weeks 1, 2, 5, and 8** at 1pm to control for time of day effects and the duration since the last morning L-DOPA dose (anticipated to be 4 hours). Processing speed will be assessed using the Digit Symbol test from the Wechsler Adult Intelligence Scale-III (WAISIII) (119) and the Pattern and Letter Comparison tests (120). These tests are all reliable and valid, with moderate to high loadings on the latent speed factor. A latent factor (and subsequent factor score) will be extracted from the 3-test battery pre- and post-treatment and used as the main outcome in the R61. By extracting a latent factor and factor loadings we will utilize a more pure measure of processing speed than if we used the raw scores from an individual test or a sum total score from the three raw scores combined (121-124).

24. Gait will be assessed as both a single and dual task (ST, DT) on a Gaitrite walkway system in the LLDC. For the ST, patients are instructed to walk at their usual or normal speed over the walking course. For the DT, patients are instructed to walk at their usual pace while simultaneously verbally listing as many animals as possible (fluency DT). In addition, a counting DT will be used in which patients are instructed to walk at their usual pace while simultaneously performing serial subtractions by threes starting at 100 (125). Patients will start and end at a point 2 meters from beginning of the course to eliminate acceleration and deceleration effects. Each ST and DT will be assessed two times with the average used in the analyses.

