### End of study procedures

26. Following the 8 week duration treatment study, endpoint assessments of depressive symptoms, processing speed, and gait speed will be made. Subjects will undergo endpoint neuropsychological testing and post-L-DOPA MRI and PET scanning.

27. Once post-treatment research procedures are completed, patients will enter 3 month open treatment period provided free of charge as described below.

You can upload charts or diagrams if any

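### No primary HRSD test is named: eight weekly contrasts are each tested at 0.05, so if any week may count as success the two-sided error is about 12-30% (7-13% if time is linear), assuming between-week correlation 0.5-0.9.

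*SAP*

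**What the plan says.** - **Hypothesis.** Hypothesis 1 (Protocol, Specific Aims and Hypotheses) predicts greater HRSD improvement on L-DOPA than on placebo. It names no week and no summary over weeks.
- **Model.** In the SAP, Aim 3.1, change in 24-item HRSD is "analyzed as a function of time, treatment group, the interaction between time and treatment, and baseline HRSD". The coding of time is not stated.
- **Tests.** The next sentence is "Contrasts of mean difference in HRSD at each week will be formed and tested".
- **Threshold.** The SAP Overview sets one rule for everything: "Tests will be two-sided and statistical significance determined at p-value < 0.05". There is no multiplicity adjustment and no testing order.
- **Schedule.** The Protocol (Assessments, items 21 and 22) has "weekly visits from Week 0-8" and states "The following measures will be collected weekly throughout the study: 24-item HRSD". Change from baseline therefore exists at Weeks 1 to 8.
- **Hints at Week 8.** After the 8-week treatment, "endpoint assessments of depressive symptoms, processing speed, and gait speed will be made" (Protocol, End of study procedures, item 26). In SAP Aim 3.2, "change scores from baseline to 8 weeks will be calculated for both processing and gait speed". Neither sentence designates a test of Hypothesis 1.
- **Power.** The SAP power statement assumes a single two-sided test at 0.05 of a treatment group difference and does not say at which week.

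**The concern.** The written analysis produces eight treatment contrasts, a treatment term and a time-by-treatment term, all eligible for p < 0.05, and nothing says which one answers Hypothesis 1. Two consequences follow.

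First, the trial's false-positive rate is undefined. It is 5% if one test decides and well above that if any favourable week can be put forward.

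Second, the plan has no rule for conflicting results. An earlier week may be significant while Week 8 is not. In Weeks 1 and 2 the L-DOPA arm is still being titrated (Protocol, Clinical treatment, item 19), so a claim could rest on data collected before the target dose was reached. Once results are known, a choice among the tests is no longer credible.

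**Working it through.** **Inputs**

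- Eight contrasts, Weeks 1-8 (Protocol, Assessments).
- Two-sided 0.05 for each, critical value 1.96 (SAP, Overview).
- 45 per arm, 15% dropout, effect size 0.60, that is 3 points over SD 5 (SAP, Power analysis). 45 × 0.85 = 38.25, taken as 38 per arm.
- Between-week correlation of HRSD change: not in the documents. **Assumed** 0.5 to 0.9, under compound symmetry (CS) and AR(1).

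**The plan's own figure.** The SAP gives more than 80% power. A two-sample t-test (noncentral t, d = 0.60, two-sided 0.05) gives 80.4% at 45 per arm and 73.3% at 38 per arm. The stated figure is thus reached without dropout, or after dropout with a variance gain the SAP does not state: a baseline correlation of about 0.4 gives 81.4% by the normal approximation. That is a separate matter. What counts here is that the calculation allows for one test, not eight.

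**Ceiling.** For independent contrasts, P(at least one) = 1 − 0.95^8 = 33.7%.

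**Categorical time.** The eight null z-statistics have correlation matrix R. The familywise error is P(max |Z| > 1.96), by simulation with 400,000 draws. The error favouring L-DOPA counts one direction only.

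| Correlation | CS, two-sided | AR(1), two-sided | CS, favouring L-DOPA | AR(1), favouring L-DOPA |
|---|---|---|---|---|
| 0.5 | 25.1% | 29.7% | 12.6% | 15.4% |
| 0.7 | 19.1% | 25.0% | 9.6% | 12.7% |
| 0.9 | 12.0% | 16.0% | 6.0% | 8.0% |

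**Linear time.** The treatment effect is then an intercept and a slope. With X = [1, week] and V the between-week covariance, the eight contrasts have covariance X(X'V⁻¹X)⁻¹X', so only two parameters vary.

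| Correlation | CS, two-sided | AR(1), two-sided |
|---|---|---|
| 0.5 | 9.4% | 12.7% |
| 0.7 | 8.1% | 12.1% |
| 0.9 | 6.7% | 10.0% |

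In the direction favouring L-DOPA the linear range is 3.4-6.5%.

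**Adding the model terms (categorical).** If the overall treatment test and the 7-df interaction test may also count, the error is 16-27% (CS) and 19-31% (AR(1)).

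**Conflict with Week 8 (categorical, no true effect).** Some Week 1-7 contrast is significant while Week 8 is not in 7-20% of trials (CS) and 11-25% (AR(1)). For Weeks 1 or 2 alone the figure is about 3-9%.

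**Price of each repair.** One pre-named test keeps error at 5%. Bonferroni over eight weeks needs 0.05/8 = 0.00625 per week. At 38 per arm and d = 0.60, simple t-test power at one week is 73% at 0.05 and 43% at 0.00625. Bonferroni is conservative for correlated weeks, and baseline adjustment would raise both figures.

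**The case against.** The SAP says the weekly contrasts will be tested. It does not say that any significant week proves efficacy. Contrasts by visit are a common follow-up to a mixed model, and the plausible deciding tests are few: Week 8, the treatment term and the interaction. On that reading the inflation is smaller. With categorical time and the same correlations, the chance that at least one of those three is falsely significant is 11-13%, and for Week 8 or the treatment term it is 6-9%. If weekly contrasts were read only after a significant interaction, the error would be 1-4%. The upper end of the headline range also needs AR(1) with adjacent correlation 0.5, which implies a Week 1 to Week 8 correlation of 0.5^7 = 0.008.

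Much of this stands. The 12-30% is conditional on an unstated success rule and an assumed correlation, and time coding alone can cut it by more than half. But the narrower readings still exceed 5% unless a gatekeeping order is supplied, and none is written. That Week 8, the treatment term and the interaction can each be defended as the obvious primary test shows the gap. The omission itself needs no assumption.

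**Conclusion.** The concern holds. Neither document designates the test that decides Hypothesis 1, and the stated rule gives eight unadjusted weekly tests plus two model terms.

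- If one test was intended: 5% error, but the test cannot be identified from the text.
- If any week may count: two-sided error of 12-30% with categorical time or 7-13% with linear time. In favour of L-DOPA it is 6-15% or 3-7%, against 2.5%.

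The ranges rest on between-week correlations of 0.5-0.9, which the documents do not give. Confidence is high in the omission; the size depends on the correlation and the coding of time. It should be fixed because it concerns the main efficacy hypothesis and cannot be repaired credibly after the results are seen.

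**What to change.** Before unblinding (the documents do not give the trial's current status), add to SAP Aim 3.1:

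> The single primary test of Hypothesis 1 is the Week 8 treatment contrast in change in 24-item HRSD from the mixed model with week as a categorical factor, at two-sided alpha 0.05. The Week 1-7 contrasts and the treatment and time-by-treatment terms are supportive, are reported with confidence intervals, and are not used to claim efficacy.

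State the covariance structure in the same place, so that the primary test is fully defined. Week 8 fits the length of treatment, the end-of-study assessments and the Aim 3.2 change window, but any one pre-named test would restore 5%. If all weeks are to stay confirmatory, specify a multiplicity adjustment instead and accept the loss of power.

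The cost is SAP wording only, with no change to data collection or sample size. The sponsor gives up the option of claiming efficacy from an earlier week alone.

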## **Criteria for Early Discontinuation**

### Criteria for Early Discontinuation

The risk of non-response or adverse events to L-DOPA during the study period is addressed by having close clinical follow up of study subjects and stringent withdrawal criteria. These criteria are (1) participant withdraws his or her consent; (2) significant clinical worsening as defined by a slowing assessment rating using the CGI-Improvement scale of 6 (worse) or 7 (much worse) for 2 consecutive visits; or (3) development of significant side effects or an adverse event. Any subjects meeting any of these criteria will be withdrawn from the study and treated clinically. Furthermore, subjects may be withdrawn if they repeatedly miss scheduled appointments or clinical worsening necessitates more intensive treatment. No treatment is currently available for slowing, so there is not a standard of care treatment to offer patients withdrawn from the study. Thus, withdrawn patients will be followed in the open treatment period, offered appropriate psychiatric treatments if they have any conditions requiring treatment (e.g., depression), and be referred to their internist for close medical follow up.

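### The arm comparison of processing and gait speed uses only baseline-to-Week-8 change, so it loses subjects without a Week 8 value and leaves the Week 1, 2 and 5 measurements unused

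*SAP*

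**What the plan says.** **Measurement.** Protocol, Study Procedures, Assessments (item 23): the baseline processing and gait speed "assessments will be repeated after Weeks 1, 2, 5, and 8 at 1pm to control for time of day effects". That gives four post-baseline values per subject for each measure.

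**Analysis of speed.** SAP, Analyses for Aim 3, Aim 3.2: "change scores from baseline to 8 weeks will be calculated for both processing and gait speed". These scores enter Pearson correlations; "two-sample t-tests will be used to assess treatment group differences"; and a regression is fitted with "change in HRSD as the outcome predicted by treatment, processing and gait speed change scores, and baseline values of processing and gait speed".

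**Analysis of HRSD.** SAP Aim 3.1 is the only place where a longitudinal model is specified: "The change in 24-item HRSD from baseline will be analyzed as a function of time, treatment group, the interaction between time and treatment", with baseline HRSD as a further term.

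**Missing data.** The SAP ties its missing-at-random statement to that mixed model. It promises pattern-mixture sensitivity analyses without naming an outcome. Its intent-to-treat set is every randomised subject with one HRSD score after baseline. It gives no rule for a missing Week 8 speed value.

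**Withdrawal.** Protocol, Criteria for Early Discontinuation, lists among the reasons "significant clinical worsening as defined by a slowing assessment rating using the CGI-Improvement scale", with a rating of 6 or 7 at two visits in a row. Subjects who meet a criterion leave the study. The End of study procedures describe endpoint speed tests after the 8-week treatment, but do not say that withdrawn subjects receive them.

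**The concern.** A t-test on Week 8 change needs a Week 8 value, so as written it is an analysis of completers, although the SAP's overview describes an intent-to-treat set. Whether L-DOPA speeds thinking and walking is a stated purpose of the trial (Protocol, Lay Summary), so this contrast will be read as a result in its own right.

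One route out of the trial is a clinician's judgement that slowing has worsened. If the drug works, that route should take more subjects from placebo than from L-DOPA. The placebo subjects who remain would then be the better ones, and the arm difference would be understated. The criterion needs ratings at two consecutive visits, so it can ordinarily not be met before Week 2. Such subjects would normally have at least a Week 1 speed value, and often Week 2 or Week 5 values. The plan collects these and does not use them.

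**Working it through.** **1. The SAP's own figure is a completer figure.** Inputs from the SAP: N = 90, 15% dropout, two-sided alpha 0.05, detectable correlation above 0.31. Power for Aim 3.2 is not stated; I assume 80%, as for Aim 3.1.

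Formula: r = tanh[(1.960 + 0.842) / √(n − 3)].

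| n | source | detectable r |
|---|---|---|
| 90 | all randomised | 0.292 |
| 77 | 90 × 0.85 = 76.5, rounded up | 0.315 |
| 76 | 76.5, rounded down | 0.317 |
| 68 | protocol's completers | 0.334 |

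The stated 0.31 fits 76 to 77 subjects, not 90. The SAP itself removes the dropouts from Aim 3.2.

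**2. How many are lost.** At 15% dropout: 90 × 0.15 = 13.5, so 13 to 14 subjects. The protocol's Description of Subject Population plans for 68 completers from 90 enrolled: 90 − 68 = 22, or 24.4%.

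**3. Illustrative size of the bias.** The documents give no speed effect, no between-visit correlation and no share of dropout due to slowing, so all of these are assumptions. Set-up:
- 45 per arm, speed change in SD units, 4,000 simulated trials per setting;
- true Week 8 arm difference 0.60, growing in proportion to the week;
- between-visit correlation 0.5, 0.7 or 0.85;
- a subject leaves before Week 8 with probability p1 if the Week 5 change is below −0.7 SD, and p2 otherwise.

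The completer estimate is the Week 8 mean difference among those observed. The alternative predicts missing Week 8 values from arm and Weeks 1, 2 and 5. Ranges are over the three correlations.

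| p1 / p2 | total loss | completer | using earlier visits |
|---|---|---|---|
| 0.15 / 0.15 (unrelated to speed) | 15% | 0.594–0.607 | 0.596–0.604 |
| 0.40 / 0.06 | 13% | 0.561–0.587 | 0.590–0.606 |
| 0.60 / 0 | 11.5% | 0.543–0.567 | 0.597–0.604 |
| 0.60 / 0.10 | 20% | 0.544–0.564 | 0.596–0.602 |

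When dropout depends on speed, the shortfall runs from 0.600 − 0.587 = 0.013 (2%) to 0.600 − 0.543 = 0.057 (about 10%). The standard error is about 0.21 to 0.23 for both methods.

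Runs with a true difference of 0.50 and similar withdrawal rules gave a completer contrast of 0.43 to 0.49. Using the earlier visits restored it to 0.50–0.51 at about the same standard error. With no true effect, both methods centre on zero.

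**4. The association analyses.** The same kind of dropout was applied with unit-variance changes, visit correlation 0.6 to 0.8, an assumed slope of 0.40, and HRSD change depending on Week 8 speed change. The completer regression slope was 0.40 against 0.40 with full data. The Pearson correlation fell from 0.40 to 0.37–0.38. The arm contrast in this check was 0.43 to 0.44 (true 0.50, standard error 0.22).

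**The case against.** **The bias is small.** This stands. The largest shortfall at a true 0.50 is 0.07 SD, about a third of a standard error (0.07 / 0.22 = 0.32). It runs toward no effect and creates no false positive.

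**The simulation favours the remedy.** Withdrawal depends on a measured Week 5 value, so a method that uses Week 5 is bound to recover the truth. The protocol's trigger is a clinician rating, not a speed score. Subjects may also leave through withdrawn consent, side effects or missed visits, in shares that the documents do not give. This stands too. A reader might infer that dropout is driven by the analysed quantity itself; the link is plausible but indirect.

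**Hypothesis 2 is not damaged.** A reader might infer that every speed analysis is biased. The documents do not support that. Hypothesis 2 and Aim 3.2 ask about association. Speed change is a predictor in the regression, and selecting on a predictor does not by itself bias its slope, as step 4 shows.

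**Temporal order.** A reader might also object that speed and HRSD change span the same eight weeks, so the plan cannot show that speed improves first. The aim is stated only as association. A lagged model would be optional, and with Week 8 HRSD as its outcome it would lose subjects without that score.

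**Pattern-mixture analyses may already cover speed.** They are not expressly limited to HRSD. But the paragraph is tied to the mixed model and gives no method for a change score, and a sensitivity analysis would not replace a completer main estimate.

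**Conclusion.** The point holds for the treatment comparison of processing and gait speed, and only there. On the text it is certain: the t-test uses one of four scheduled post-baseline values and loses anyone without it, 13 to 14 or 22 of 90 depending on which of the documents' dropout figures applies. The resulting bias is possible and modest. It was 0.01 to 0.07 SD on a true 0.50 under assumed correlations and withdrawal rules, and nil if dropout is unrelated to speed. Its real size cannot be derived from the documents. The gain from the earlier visits is mainly in bias, with little change in precision. The primary HRSD analysis is unaffected, and the Hypothesis 2 correlation and regression may stay as planned. The change is worth making because the SAP already uses the better method for HRSD and the data are already scheduled.

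**What to change.** In SAP Aim 3.2, for the arm comparison of each speed measure, replace the two-sample t-test with a repeated-measures mixed model:
- outcome: change from baseline at Weeks 1, 2, 5 and 8;
- terms: visit, treatment, visit-by-treatment and baseline speed;
- population: all randomised subjects with any speed value after baseline;
- estimate: the Week 8 treatment contrast.

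Treat visit as categorical, because Weeks 1 and 2 fall during titration and a straight-line trend should not be imposed.

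State that the processing-speed factor score uses the same loadings at every visit. The protocol describes its extraction only before and after treatment, so a rule for the intermediate visits is needed.

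Extend the planned pattern-mixture sensitivity analysis to this Week 8 contrast, since the mixed model still rests on missing at random and the withdrawal rating may carry information that the speed scores do not.

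Cost: SAP wording, one more model per speed measure and the scoring rule. No new visits or data are needed.

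### SAP Aim 3.2 plans both a pooled, unadjusted correlation and a treatment-adjusted regression, does not say which decides Hypothesis 2, and states power only for the pooled correlation, which can be non-zero with no within-arm link

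*SAP*

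**What the plan says.** The protocol's Specific Aims section states, as Hypothesis 2, that larger post-L-DOPA gains in processing and gait speed go with larger improvement in depressive symptoms. (It also covers raclopride binding, which is not at issue here.) The SAP takes up the speed part as Aim 3.2 and lists two analyses of association.

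- First, a correlation: "Pearson correlation among all change scores, including change in HRSD will be examined". No stratification or adjustment by arm is mentioned.
- Second, a regression: "Multivariate linear regression models will be fit with change in HRSD as the outcome predicted by treatment, processing and gait speed change scores", together with the baseline values of processing and gait speed. Baseline HRSD is not in this model, although the Aim 3.1 model for the same HRSD change includes it.

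The SAP does not rank the two. Its power paragraph covers only a correlation: "With N=90, assuming a drop out of 15%, we would be able to detect correlations >0.31". The general rule in the SAP Overview is "Tests will be two-sided and statistical significance determined at p-value < 0.05".

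**The concern.** Hypothesis 2 is a claim about mechanism: patients whose speed improves more should be the patients whose mood improves more. A correlation pooled over the two arms mixes that patient-level association with the difference between the arm means. If L-DOPA improves speed on average and lowers HRSD on average, the treated patients sit in one corner of the scatter plot and the placebo patients in the other. A correlation then appears even if, within each arm, speed change says nothing about HRSD change. This is the very situation the trial hopes for.

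The regression removes that component because treatment is in the model. But the two analyses can disagree, and nothing written in advance settles which one stands. Because the power statement is given for the pooled correlation, a reader could take the pooled correlation as the test of the hypothesis.

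**Working it through.** **Inputs.** From the SAP: N=90, 45 per arm, 15% dropout, two-sided 0.05. On the HRSD effect it says "we have >80% power to detect treatment group differences with ES = 0.60 or greater" and, with an SD of 5, "this ES would correspond to a change in HRSD of 3 points", which is 3/5 = 0.6 SD. Its meaningful change of 4 points is 4/5 = 0.8 SD. Assumed: 80% power for Aim 3.2 (the SAP gives a power level only for Aim 3.1), equal variances in the arms, and the effect on speed, which neither document gives and which is therefore shown as a range.

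**1. Reproduce the stated 0.31.** By Fisher's z, the detectable r is tanh[(1.960 + 0.842)/√(n − 3)], with n = 90 × 0.85 = 76.5.
- n=76: tanh(2.802/√73) = 0.317
- n=77: tanh(2.802/√74) = 0.315
- One arm of 38: tanh(2.802/√35) = 0.44

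The SAP's figure is reproduced to within rounding (power at exactly 0.31 is 78% to 79%), and only with the arms pooled.

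**2. Correlation induced by pooling.** For 1:1 allocation, within-arm correlation ρ, and treatment effects dx (speed) and dy (HRSD improvement) in within-arm SDs:

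pooled r = (ρ + dx·dy/4) / √[(1 + dx²/4)(1 + dy²/4)].

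Signs are set so that improvement is positive on both outcomes. With ρ = 0 and 0.6 SD on both, r = 0.09/1.09 = 0.083. With 0.8 SD on both, r = 0.16/1.16 = 0.138.

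**3. Rejection rate at the 5% level, n=76, ρ = 0.** The normal approximation is Φ(m − 1.96) + Φ(−m − 1.96), with m = atanh(r)·√73. For 0.6/0.6, m = 0.707 and the rate is 0.105 + 0.004 = 0.109. The simulations use 38 per arm and 50,000 runs per row.

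| Speed / HRSD effect (SD) | Induced r | Approximation | Simulated, pooled | Simulated, treatment-adjusted |
|---|---|---|---|---|
| 0 / 0 | 0 | 5.0% | 5.1% | 5.2% |
| 0.3 / 0.6 | 0.043 | 6.5% | 6.55% | 5.0% |
| 0.6 / 0.6 | 0.083 | 10.9% | 11.2% | 5.1% |
| 0.8 / 0.8 | 0.138 | 22.0% | 22.5% | 5.1% |

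The treatment-adjusted column is a partial correlation given arm for one speed measure.

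**4. When ρ is not zero.** Pooling can move r either way.
- ρ = 0.31, effects 0.6/0.6: pooled r = 0.367 (raised)
- ρ = 0.31, effects 1.0/0.1: pooled r = 0.299 (lowered)
- ρ = 0.60, effects 0.6/0.1: pooled r = 0.588 (lowered)

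**5. Cost of moving the power statement.** For a partial correlation given k other regressors, replace n − 3 by n − 3 − k, at n=76.
- Treatment only (k=1): 0.319
- The SAP's other four regressors for one speed coefficient (k=4): 0.325
- These plus baseline HRSD (k=5): tanh(2.802/√68) = 0.327

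**The case against.** The strongest reply is that the SAP already contains the right model. The sentence that plans the regression includes treatment, so the association net of arm will be estimated whatever the pooled correlation shows. The correlations are only to be examined, which is how one describes a descriptive matrix, and nothing ranks them above the regression. Much of this stands: a reader might infer that Aim 3.2 rests on the pooled correlation alone, and the documents do not support that. What remains is that neither analysis is named as decisive and the power claim is attached to the unadjusted one.

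A second reply is that the artefact is small: 0.08 against a planned 0.31. It is true that arm effects alone would need about 1.34 SD on both outcomes to reach 0.31. But 0.31 is the true correlation detectable with adequate power, not the significance threshold, which is about 0.23 at n=76. A shift of 0.08 is enough to take a 5% test to about 11%.

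A third reply is that if L-DOPA improves both outcomes, a pooled association is real, so calling it a false positive presumes a null that the SAP does not state. That is fair. The rejection rates above are errors only against the null of no within-arm association. That is the null relevant to a patient-level claim about who improves, but the SAP should say so.

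**Conclusion.** The point holds as a gap in specification with a modest, quantifiable consequence. Under no within-arm link at n=76, the pooled test rejects about 6.5% to 11% of the time with the SAP's 0.6 SD on HRSD and an assumed 0.3 to 0.6 SD on speed, and about 22% with 0.8 SD on both. Adjustment for treatment holds it near 5%.

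Two stronger readings should be resisted. A reader might infer that the pooled correlation is inflated whenever L-DOPA works on both outcomes. That is not so: with a within-arm correlation and unequal effects, pooling can lower r slightly. A reader might also infer that the error rate at least doubles in general. It does so at 0.6 SD on both outcomes, but not with a speed effect of 0.3 SD, and the documents give no speed effect to choose between them.

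The figures rest on equal within-arm variances, 38 patients analysed per arm, and 80% power assumed for Aim 3.2. If only the 68 completers named in the protocol's subject population section were analysed, the detectable pooled r would be 0.334 instead of 0.317.

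**What to change.** In the SAP, under Aim 3.2:

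- Name the processing- and gait-speed change coefficients from the planned treatment-adjusted regression as the test of Hypothesis 2.
- Add baseline HRSD to that model. It is already collected and already used in Aim 3.1 for the same outcome. The documents do not allow the gain in precision to be quantified.
- Label the pooled Pearson correlations descriptive.
- In the power paragraph, state the power level and replace the raw correlation with a detectable partial correlation: at n=76 and 80% power, about 0.32 adjusting for treatment only and about 0.33 with all covariates including baseline HRSD.

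The cost is a few sentences and a few degrees of freedom. The full model has six regressors and so 76 − 7 = 69 residual degrees of freedom, against 74 for a raw correlation. The detectable correlation rises from 0.317 to at most 0.327. No new data are needed.
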